6.0 Risks

[figure not shown]
This study will evaluate the addition of oral dapagliflozin to standard-of-care heart failure therapies in patients with hypervolemic heart failure. We do not expect the risk of the dapagliflozin treatment arm will be different than the standard of care treatment arm. Dapagliflozin has a lower hypoglycemia risk than standard of care insulin therapy. Study procedures are designed to manage and minimize risks through careful selection of the patients who participate in the trial. We have developed a standardized protocol for diabetic therapies with endocrinology to minimize hypoglycemia risk in patients with diabetes. Participants will be monitored throughout the treatment phase of the study, throughout hospitalization, and at 30-day follow-up. Further, an independent DSMB will monitor safety of the participants throughout the study.

7.0 Reporting of Adverse Events or Unanticipated Problems involving Risk to Participants or Others

An Adverse Event (AE) is the development of an undesirable medical condition or the deterioration of a pre-existing medical condition following or during exposure to a

pharmaceutical product, whether or not considered causally related to the product. An undesirable medical condition can be symptoms (eg, nausea, chest pain), signs (eg, tachycardia, enlarged liver) or the abnormal results of an investigation (eg, laboratory findings, electrocardiogram). In clinical studies, an AE can include an undesirable medical condition occurring at any time, including run-in or washout periods, even if no

study treatment has been administered. The term AE is used to include both serious and non-serious AEs. The time period of AE evaluation in this study will start after signature of the informed consent and will conclude at the end of the follow up period 30 days after hospital discharge.

7.1 Safety Standards

The determination of adverse event severity rests on medical judgment of a medically qualified investigator. The severity of AEs will be graded using the following definitions:

- *Mild:* awareness of sign, symptom, or event, but easily tolerated;
- *Moderate*: discomfort enough to cause interference with usual activity and may warrant intervention;
- Severe: incapacitating with inability to do usual activities or significantly affects clinical status, and warrants intervention.

A Serious Adverse Event (SAE) is an adverse event that:

- Results in death
- Is life-threatening

- Requires prolongation of hospitalization which is not specifically required by the protocol nor is it elective
- Results in permanent impairment of a body function or permanent damage to a body structure
- Requires medical or surgical intervention to preclude permanent impairment of a body function or permanent damage to a body structure

[figure not shown]
Additionally, important medical events that may not result in death, be life-threatening, or prolong hospitalization may be considered SAEs when they jeopardize the patient or require medical or surgical intervention to prevent one of the serious outcomes listed above. Example of such medical events include: allergic bronchospasm requiring intensive treatment in an emergency room or at home, blood dyscrasias or convulsions that do not result in prolonged hospitalization, or the development of drug dependency or drug abuse. Medical and scientific judgment must be exercised when classifying events as serious.

Serious Adverse Events (SAE) related to dapagliflozin will be categorized as:

- Suspected Unexpected Serious Adverse Reaction (SUSAR):
 - unintended response to dapagliflozin, which is not listed in the applicable product labeling, and meets the severity definition(s) of a SAE as above
- Suspected Serious Adverse Reaction (SSAR):
 - unintended response to dapagliflozin, which is listed as a potential adverse reaction in the product labeling, and meets the severity definition(s) of a SAE as above

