- Amount of total daily insulin doses (units) utilized per day during therapy among patients with type 2 diabetes, compared between treatment arms and to a prior to enrollment outpatient insulin regimen
- serum potassium covariate adjusted for baseline with attention to both elevation and depression

Single-Center Exploratory Outcomes at Vanderbilt University Medical Center

The following exploratory outcomes will only be performed in patients at Vanderbilt University Medical Center who elect to participate in a sub-study. Patients can decline to participate in this sub-study and still participate in parent clinical trial. To explore changes in the plasma proteome during IV diuresis, we will collect one 15mL blood sample (10mL in purple top EDTA tube and 5mL in red top tube) at baseline and on the final study day (Day 5 or discharge).

2.4 Safety Outcomes: Compared between treatment arms during the index stay from signing of informed consent to hospital discharge

- Change in the estimated Glomerular Filtration Rate by the MDRD equation at discharge adjusted for baseline
- Incidence of ketoacidosis, identified by the study team as elevated ketones in the urine and an arterial blood pH < 7.35 and adjudicated by the Clincal Events Committee
- Serum glucose covariate adjusted for baseline with attention to both elevation (> 400mg/dl) and depression (< 70mg/dl)
- Potential prolonged hospitalization as a result of hypoglycemia requiring medical intervention as adjudicated by the Clinical Events Committee
- Potential prolongation of hospitalization as a result of incidence of hypovolemic hypotension, defined as a symptomatic hypotension with a sustained systolic blood pressure less than 90 mmHg over 30 minutes and requiring medical intervention as adjudicated by the Clinical Events Committee. All hypotension episodes requiring medical intervention will be evaluated by the Clinical Events Committee.
- Inpatient mortality

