7.2 Adjudication and Reporting of Re-hospitalizations during the 30-day follow-up period

We will evaluate all re-hospitalizations occurring 30-days from the date of discharge from index hospitalization during which the study occurred. Thirty-day rehospitalizations are very common and expected in patients with heart failure. The purpose of this is to clarify if the hospitalization is a study outcome, AE, or both.

**Definitely or possibly related to study drug* = the rehospitalization was related to known or potential adverse events from dapagliflozin as defined in the U.S. marketed dapagliflozin package insert or according to investigator judgement in accordance with Section 7.3 below.

Rehospitalizations that are within 7 days of the last study day and are definitely/possibly related to the study drug will be reported as Adverse Events according the procedures detailed in protocol Section 7.4. All other rehospitalizations will be documented as study outcomes and adjudicated by the CEC according to protocol Section 5.4.

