7.4 Reporting of Adverse Events and SAEs

All adverse events occurring from signing of the Informed Consent through the 30-day follow-up period will be collected and reported. The Site Investigator is responsible for monitoring the safety of patients enrolled into the study. The following adverse events are anticipated, disease related-events in patients with decompensated heart failure; however, they should still be reported on the Adverse Event form in the REDCAP Database (some may require reporting as study endpoints):

- New Ventricular Arrhythmia: Ventricular tachycardia lasting longer than 30 seconds, or frequent non-sustained VT causing hemodynamic instability with MAP < 60 mmHg requiring intervention or > 1 intra-cardiac defibrillation or external cardiac defibrillation shock or ventricular fibrillation requiring defibrillation or requiring transfer to the intensive care unit
- Hypotension: SBP < 90 for 2 repeated measurements within 30 minutes or lasting at least 30 minutes or symptomatic hypotension necessitating clinical intervention (defined as vasopressor support, intravenous fluid boluses, or initiation of inotropes)
 - Hypovolemic hypotension: subset of "hypotension" requiring fluid administration for hypovolemia
- *Cardiac arrest*: any ventricular arrhythmic or pulseless electrical event that requires immediate life-sustaining medical therapies
- Acute kidney injury requiring renal replacement therapy: an acute renal failure event that began during the study period and necessitates new renal replacement therapy during the hospitalization
- Prolonged hospitalization as a result of the following safety outcomes: hypotension requiring medical intervention or hypoglycemia requiring medical intervention
- Diabetic ketoacidosis as adjudicated by the CEC
- Death

All serious adverse events must be recorded in the Adverse Event Record of the patient's REDCAP database. All serious adverse events should be monitored until stabilization or resolution.

The process of reporting of SAEs will be as follows:

- 1. The investigator team informs the site investigator of an SAE
- 2. The site investigator reports the SAE to the local IRB and to the coordinating center and PI within 24 hours of being aware of the event. The site investigator will electronically submit the necessary supporting documentation to the coordinating site.
- 3. The coordinating center and PI will report the SAE to AstraZeneca.

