7.6 Non-serious Adverse Events

Non-serious AEs will be reported to the IRB and AstraZeneca in annual scheduled reports. Additionally, the investigator will notify AstraZeneca of all non-serious AEs as a line item list at the end of the study. Non-serious AEs will be presented to the DSMB at each interim analysis.

The following events are examples of potential non-serious suspected adverse reactions unless the seriousness meets criteria for a SAE as defined above.

- Incidence of mycotic genital infection, defined as a new symptomatic infection requiring treatment
- Incidence of symptomatic cystitis, defined as new symptoms of dysuria, frequency, and/or urgency, plus a urine culture with at least 10² colony forming units of a uropathogen requiring treatment with antibiotic therapy
- Incidence of symptomatic pyelonephritis, defined as new symptoms of dysuria, frequency, and/or urgency plus acute flank pain, plus a urine culture with at least 10² colony forming units of a uropathogen requiring treatment with antibiotic therapy

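### The SAE criteria leave out new hospitalization, and the 7-day limit on drug-related readmissions in Protocol 7.2 conflicts with the 30-day AE window in 7.0 and 7.4

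*Protocol*

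**What the plan says.** **Seriousness (Protocol 7.1).** Five SAE criteria are listed: death, threat to life, a prolonged stay, permanent impairment or damage, and intervention to prevent such harm. The one that concerns hospital care reads: "Requires prolongation of hospitalization which is not specifically required by the protocol nor is it elective". A further paragraph covers events short of the list: "important medical events that may not result in death, be life-threatening, or prolong hospitalization may be considered SAEs", subject to medical judgement.

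**AE window (Protocol 7.0 and 7.4).** AE evaluation starts at consent and "will conclude at the end of the follow up period 30 days after hospital discharge". Section 7.4 agrees: "All adverse events occurring from signing of the Informed Consent through the 30-day follow-up period will be collected and reported".

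**Readmissions (Protocol 7.2 and 5.4).** Section 7.2 evaluates every readmission in the 30 days after index discharge. Those that fall "within 7 days of the last study day and are definitely/possibly related to the study drug" are reported as AEs under 7.4. All the rest are documented as outcomes and sent to the CEC under 5.4. Section 5.4 lists only readmissions for heart failure or diabetes.

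**What SAE status triggers (Protocol 7.4 and 7.6).** An SAE goes to the local IRB, the coordinating center and the principal investigator within 24 hours, then to the drug company, and to the FDA if it is a SUSAR. Events below that threshold follow a slower path: "Non-serious AEs will be reported to the IRB and AstraZeneca in annual scheduled reports".

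**The concern.** After discharge there is no index stay left to prolong, so the only hospital-related criterion in 7.1 cannot apply in the ordinary way. Yet a new admission is the form in which a serious post-discharge event would usually appear. Section 7.2 then sets its own, shorter window for exactly these events.

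Fast reporting is at stake. The 24-hour notices, case reports to the drug company, SUSAR assessment and off-schedule alerts to the DSMB all depend on an event being classed as an SAE. The prespecified safety outcomes in Protocol 2.4 stop at hospital discharge, so AE reporting is the main safety route after that. Protocol 2.1 also says the study should help establish the safety of starting the drug in hospital even if the primary endpoint is not met.

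**Working it through.** The plan states no figure to reproduce. The check compares the rules and counts days.

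**1. Is new hospitalization a seriousness criterion anywhere?** It is not among the five items in 7.1. A line lost in text extraction is unlikely, because the next paragraph restates the list in terms of prolonged hospitalization. The remaining routes to SAE status for a readmission are death, threat to life, permanent harm, intervention to prevent it, or the clause for important medical events, which is permissive.

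**2. How much of the 30 days does the 7.2 rule reach?** Inputs are the 30-day window after discharge (7.0, 7.4) and the 7-day limit (7.2). Let k be the number of days from the last study day to discharge. Then:

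covered post-discharge days = max(0, 7 − k), out of 30

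| Reading of the last study day | Covered | Outside the rule |
|---|---|---|
| Day of discharge (k = 0) | 7/30 = 23.3% | 23/30 = 76.7% |
| Day 5, discharged 3 days later (k = 3) | 4/30 = 13.3% | 26/30 = 86.7% |
| Day 5, discharged 7 or more days later (k ≥ 7) | 0/30 | 30/30 = 100% |

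The first row is the most generous of these readings. The other two assume that the last study day is Day 5 for a patient who stays longer. Section 5.1 (treatment until 5 days or discharge) and the proteomic sub-study paragraph before 2.4 suggest this, but 7.2 does not say so. The k values are illustrative, since the documents give no distribution of length of stay. Reading the last study day as the 30-day call would make the limit exclude nothing, so it is hardly what was meant.

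**3. Trace one event through the rules.** Take a dapagliflozin patient readmitted with pyelonephritis 10 days after discharge, judged possibly related. Section 7.6 names this condition as a potential suspected reaction.

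- Under 7.0 and 7.4 the illness is an AE and is reportable.
- Under 7.2 the readmission is past day 7 even with discharge as the anchor, so it is handled as an outcome and sent to the CEC.
- Under 5.4 the CEC reviews heart failure and diabetes readmissions, so this one is outside its remit.
- Under 7.1 the admission does not make the event serious. Section 7.6 treats it as non-serious unless an SAE criterion is met.

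On post-discharge day 5 with the same anchor, 7.2 would send the readmission to 7.4. Whether the 24-hour steps there apply would still turn on 7.1.

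**The case against.** The strongest reply is that little is actually lost. Section 7.4 collects all AEs to day 30, and Appendix A schedules an AE assessment at that contact. The definition in 7.0 makes the illness an AE whatever its cause, and 7.2 only classifies the readmission. The DSMB sees AE reports at each meeting and non-serious AEs at each interim analysis. Unexpected AEs of either kind go promptly to the IRB. Ketoacidosis or urosepsis may well qualify as life-threatening or under the discretionary clause. All-cause 30-day readmission is compared by arm (SAP, Exploratory Analyses). A limited window after the last dose is also a defensible filter in a population that is often readmitted. Finally, 7.2 has a starred definition with no visible referent and a figure nearby was not available to this review, so a chart may settle the routing.

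Much of this stands, and it rules out stronger readings. A reader might infer that most of the 30-day safety window goes unreported; 7.4 says otherwise. A reader might infer that the day-10 pyelonephritis is not an AE at all, or that the DSMB would not see it; the documents support neither. Nor do they say that a related readmission within 7 days goes to the annual list, since 7.2 sends it to 7.4.

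The reply does not remove the two written gaps. The list in 7.1 still omits admission. The case for a filter is weak because 7.2 already requires relatedness and 7.3 already weighs timing. The 7-day limit therefore overrides an investigator who has judged the event possibly related.

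**Conclusion.** The point holds in two parts.

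First, a possibly drug-related readmission is not an SAE because it is an admission. Unless it meets another criterion or the discretionary clause is used, it stays off the 24-hour route.

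Second, 7.2 conflicts with 7.0 and 7.4. With discharge as the anchor, 23 of 30 post-discharge days lie outside its rule; with Day 5 as the anchor and a longer stay, more do. Later readmissions for reasons other than heart failure or diabetes are sent to a committee whose remit excludes them.

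The day counts are shares of calendar time, not of events, and apply only to drug-related readmissions. The conclusion rests on the written text, without the figure. It does not touch the primary or secondary efficacy analyses or the safety outcomes in 2.4, which end at discharge. It should be corrected because it governs how quickly post-discharge harm is escalated.

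**What to change.** - **7.1:** add new inpatient hospitalization after index discharge to the SAE criteria. Make an explicit exception for heart failure readmissions judged unrelated, which are recorded as outcomes.
- **7.2:** replace the 7-day limit with the AE window already in 7.0 and 7.4, 30 days after hospital discharge. Readmissions judged possibly related are then reported through 7.4 as well as recorded as outcomes. This covers 30 of 30 days and removes the need to define the last study day.
- **Alignment:** make the referral to the CEC in 7.2 match 5.4, and use the causality terms of 7.3, which has no category for definitely related. If a chart accompanies 7.2, change it too.

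The cost is protocol wording, an edit to the REDCap form and a few more SAE reports. No new contact is needed, because Appendix A already schedules AE and outcome assessment at 30 days.

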7.2 Adjudication and Reporting of Re-hospitalizations during the 30-day follow-up period

We will evaluate all re-hospitalizations occurring 30-days from the date of discharge from index hospitalization during which the study occurred. Thirty-day rehospitalizations are very common and expected in patients with heart failure. The purpose of this is to clarify if the hospitalization is a study outcome, AE, or both.

**Definitely or possibly related to study drug* = the rehospitalization was related to known or potential adverse events from dapagliflozin as defined in the U.S. marketed dapagliflozin package insert or according to investigator judgement in accordance with Section 7.3 below.

Rehospitalizations that are within 7 days of the last study day and are definitely/possibly related to the study drug will be reported as Adverse Events according the procedures detailed in protocol Section 7.4. All other rehospitalizations will be documented as study outcomes and adjudicated by the CEC according to protocol Section 5.4.

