	Day 5 or Discharge: standing weight, NT-proBNP, BMP, vital signs, urine output quantification, document HF and diabetic medications, congestion score, outcomes assessment, remind primary team to schedule standard-of-care 3-7-day follow-up visit with endocrinology (if patient has diabetes) and HF			
	30-day phone follow-up : document HF and diabetic medications, outcomes assessment			
Study Duration	Enrollment is anticipated to occur over 14 months with the end of study occurring at hospital discharge and a 30-day phone-call follow-up			
Clinical Event Committee	The following events will be adjudicated by a Clinical Event Committee blinded to patient assignment:			
	 Worsening heart failure defined as inpatient administration of an IV inotrope with dobutamine, milrinone, or dopamine, new admission to an intensive care unit, new non-invasive positive pressure ventilation with bilevel positive airway pressure, or increase in the IV diuretic protocol intensity by 2 rows after Study Day 1 30-day hospital readmissions due to heart failure or diabetes- related events 			

	 Prolonged hospitalization as a result of hypoglycemia requiring medical intervention Prolonged hospitalization as a result of hypotension requiring medical intervention In-hospital incidence of ketoacidosis Inpatient mortality
Data and Safety Monitoring Board	An independent Data and Safety Monitoring Board will advise the principal investigator on safety aspects and overall progress of the study.

Table of Contents:

- **1.0** Background and rationale
- 2.0 Study outcomes
- 3.0 Inclusion/Exclusion criteria
- 4.0 Patient screening, consent, and randomization
- 5.0 Study Procedures
- 6.0 Risks
- 7.0 Reporting of adverse events
- 8.0 Data collection and record keeping
- 9.0 Study withdrawal
- 10.0 Statistical methods
- 11.0 References

1.0 Background and Rationale:

Patients with acute decompensated HF (ADHF) are generally admitted due to symptoms of congestion and 90% are treated with a loop diuretic.¹ However at least one-third of these patients are inadequately decongested due primarily to "diuretic resistance" and/ or "cardiorenal syndrome".^{2,3} The inability to achieve decongestion is associated with a worse prognosis and a higher rate of re-hospitalization for ADHF.² More than 40% of all patients admitted with ADHF have diabetes and that percentage is growing both in Heart Failure with Reduced Ejection Fraction (HFrEF) and Preserved Ejection Fraction (HFpEF).⁴

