5.4 Clinical Event Committee

The CEC will consist of 3 independent clinicians, which will consist of at least one endocrinologist and at least one heart failure specialist. The members of this committee

will be independent of the study implementation teams and will be blinded to study arm assignment. This committee will review abstracted clinical data to determine when primary endpoints and major events have occurred. The CEC will review data for the following study outcomes:

- Potential inhospital worsening heart failure events identified by the following criteria:
 - New intravenous inotropic therapy
 - New admission to an intensive care unit
 - New non-invasive positive pressure ventilation with bilevel positive airway pressure
 - 2 or more increases in IV diuretic protocol intensity after Study Day 1
- 30-day readmission events for heart failure or diabetes-related care
- Prolonged hospitalization as a result of the following safety outcomes: hypotension requiring medical intervention or hypoglycemia requiring medical intervention
- In-hospital incidence of ketoacidosis
- Inpatient mortality for causality

All criteria and definitions will be pre-specified in detail in the Clinical Events Committee Charter. Only outcomes adjudicated as such by the Clinical Events Committee will be considered. If there are valid reasons for questioning an adjudication, such as an inexplicable outlier during analysis, the Principal Investigator may formally request a review of the case. In such situations, the Clinical Events Committee has final determination.

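### Protocol 7.2 sends early dapagliflozin-related readmissions to adverse-event reporting and only the rest to the CEC, so read literally it can remove events from secondary endpoint (b) in one arm

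*Protocol*

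**What the plan says.** Protocol 7.2 covers every rehospitalisation within 30 days of index discharge and gives its aim: "The purpose of this is to clarify if the hospitalization is a study outcome, AE, or both". Two operative sentences follow.

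- Rehospitalisations "within 7 days of the last study day and are definitely/possibly related to the study drug will be reported as Adverse Events", under Protocol 7.4.
- The remainder: "All other rehospitalizations will be documented as study outcomes and adjudicated by the CEC according to protocol Section 5.4".

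A starred definition in 7.2 treats a readmission as drug-related if it was "related to known or potential adverse events from dapagliflozin" as listed in the US package insert, or if the investigator judges it so under 7.3.

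Protocol 5.4 gives the CEC "30-day readmission events for heart failure or diabetes-related care" without exception. It adds: "Only outcomes adjudicated as such by the Clinical Events Committee will be considered". The protocol summary says the committee works blinded: "The following events will be adjudicated by a Clinical Event Committee blinded to patient assignment". Protocol 2.2 and the SAP (Secondary Endpoints, b) define the endpoint as CEC-adjudicated readmission, with no carve-out for drug-related events. The SAP (Secondary Analyses, b) analyses it by a Cox model stratified by site, and has no rule for readmissions reported as adverse events.

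**The concern.** The two sentences in 7.2 divide rehospitalisations into two groups, and neither group is described as going to both places. A reader who follows them literally does not send an early, drug-related readmission to the CEC. Under 5.4 it then does not count.

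The filter is not neutral between arms. Relatedness is framed in terms of dapagliflozin, which only one arm receives as study drug, and it is judged by an investigator who knows the allocation. An unblinded, arm-dependent decision would therefore come before the blinded committee for one of the trial's two secondary endpoints. Any event lost this way favours dapagliflozin.

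**Working it through.** **The texts side by side**

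1. The aim of 7.2 allows three classes: outcome, adverse event, both.
2. The operative rule in 7.2 supplies two: early and related goes to adverse-event reporting; everything else goes to the CEC as an outcome. The third class is empty.
3. The CEC remit (summary and 5.4) and the endpoint definition (2.2 and SAP) include all heart-failure or diabetic readmissions within 30 days.
4. Under 5.4, an event the CEC does not adjudicate is not counted.
5. Steps 2 and 4 together remove some events that step 3 includes.

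**Which events could be affected**

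The event must be a heart-failure or diabetic readmission, judged related to dapagliflozin, and within 7 days of the last study day. Protocol 7.3 calls an event possibly related only if underlying conditions do not sufficiently explain it. That makes diabetic readmissions more plausible candidates than heart-failure ones.

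I take the last study day as day 5 or discharge, whichever is earlier (Protocol 2.3, single-centre sub-study). For discharge on study day L, the post-discharge days inside the window are max(0, 7 − (L − min(5, L))). This gives 7 days for L ≤ 5, 4 days for L = 8, and none for L ≥ 12.

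**Possible size**

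The documents give no readmission rate and no number of diverted events, so there is no stated figure to reproduce. The rates and k below are assumptions, with 120 patients per arm (from the documents) and no true effect.

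- E = rate × 120 patients with an event in each arm; k = dapagliflozin patients whose event never reaches the CEC.
- RR = (E − k)/E.
- SE(log RR) = √(1/(E − k) − 1/120 + 1/E − 1/120).
- Shift = |ln RR|/SE.

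Example, E = 12 and k = 2: RR = 10/12 = 0.833; SE = √(1/10 − 1/120 + 1/12 − 1/120) = 0.408; shift = 0.182/0.408 = 0.45.

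| Rate (E) | k = 1: RR, shift | k = 2: RR (95% CI), shift | k = 5: RR, shift |
|---|---|---|---|
| 10% (12) | 0.917, 0.22 | 0.833 (0.37 to 1.85), 0.45 | 0.583, 1.18 |
| 15% (18) | 0.944, 0.18 | 0.889 (0.48 to 1.66), 0.37 | 0.722, 0.96 |
| 20% (24) | 0.958, 0.16 | 0.917 (0.54 to 1.54), 0.33 | 0.792, 0.84 |

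Because the SAP uses a Cox model, an approximate hazard ratio is ln(1 − (E − k)/120)/ln(1 − E/120), assuming a constant hazard and ignoring death. For k = 2 it is 0.826, 0.881 and 0.908 at the three rates.

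No case in the table reaches p < 0.05; the most extreme (5 of 12 lost) gives p = 0.24. That describes the expected result, not the error rate. If 10% of dapagliflozin-arm events were diverted (1.2, 1.8 or 2.4 events), the chance of a nominally significant result favouring dapagliflozin is Φ(z − 1.96), with z = (p₁ − p₂)/√(p₁(1 − p₁)/120 + p₂(1 − p₂)/120) and p₂ = 0.9p₁. It rises from 2.5% to 4.5%, 5.2% and 5.9%. With no diversion there is no bias.

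**The case against.** The strongest reply is that 7.2 never says an event reported as an adverse event is withheld from the CEC. The section sits in the safety-reporting chapter, undertakes to evaluate all rehospitalisations and expressly allows both classifications. Every passage that defines the endpoint or the committee's remit is free of exceptions. Protocol 7.4 already lists CEC-adjudicated ketoacidosis for the adverse-event form, so double reporting is familiar to this protocol. The starred definition in 7.2 has no matching mark in the text available, so a flow chart with a branch for both may be missing. The committee's charter is also unseen: "All criteria and definitions will be pre-specified in detail in the Clinical Events Committee Charter". Most of this stands, and it is why the point is a contradiction rather than a proven exclusion. If a chart or charter does provide dual routing, however, the sentence about the remainder conflicts with it and still needs correcting.

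The affected set is also narrow. Relatedness under 7.3 rules out most heart-failure readmissions, and patients with type 1 diabetes or previous ketoacidosis are excluded from the trial. A patient whose first readmission is diverted may still count through a later one. All of that stands and keeps the likely effect small.

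Two further arguments are weaker. Protocol 7.3 names furosemide as well as dapagliflozin, but only in judging expectedness, not causality, so the filter remains essentially one-sided. All-cause readmission needs no CEC adjudication and may show a diverted event, but it is an exploratory endpoint and does not repair endpoint (b).

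**Conclusion.** The concern holds. As written, the routing rule in 7.2 is inconsistent with its own stated aim, with 5.4, and with the definition of secondary endpoint (b). Followed literally, it lets an unblinded relatedness judgement remove events in essentially one arm, in the direction that favours dapagliflozin.

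The size is unknown and probably small; zero is possible. The illustration for one or two patients lost is not a bound and rests wholly on assumed rates and losses. The primary endpoint, sample size and alpha are untouched. The point should be fixed because the possible bias has a known direction and the correction is cheap. Confidence is medium, because the charter and a possible flow chart could not be seen.

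**What to change.** Replace the sentence on the remaining rehospitalisations in Protocol 7.2 with a rule to this effect: every rehospitalisation within 30 days of index discharge, in both arms, is sent to the blinded CEC regardless of relatedness or adverse-event status; adverse-event reporting is additional and does not remove an event from the endpoint.

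Bring 7.2 (text and any flow chart), 5.4 and the CEC Charter into line with that rule. The relatedness terms could be aligned at the same time, since 7.2 uses a definite category that 7.3 does not define.

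The cost is one or two sentences and a few more cases for the existing committee. No new data are needed.
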